## 1.0 Research Design

### 1.1 Purpose/Specific Aims

Femoroacetabular Impingement (FAI) is a common cause of hip and groin pain in both adolescents and adults. The first line treatment of FAI is most commonly non-surgical, with an emphasis on core, gluteal, and lower back strengthening. When physical therapy and other non-operative modalities are not successful in relieving pain, hip arthroscopy is indicated, and has been shown to have a high rate of success in relieving groin pain and returning patients to their sport.

Blood flow restriction (BFR) is an adjunct to traditional physical therapy that continues to grow in popularity and evidence for its efficacy in the literature. BFR is increasingly being utilized to treat operative and non-operative conditions in physical therapy and athletic training settings. BFR involves adding a non-occlusive tourniquet to the arm or leg to partially occlude the arterial and fully occlude the venous flow during exercise. Compression of the vasculature results in muscle hypoxia, blood pooling, and increased intramuscular pressure below the cuff. This results in increased muscle strength and hypertrophy, which has a benefit in the treatment of conditions with muscle weakness and asymmetry such as FAI.

Although traditionally used to enhance muscle hypertrophy distal to the site of occlusion, there has been literature to support a proximal benefit in the upper extremity. We propose studying the results of BFR attached to the mid-thigh on the outcomes of FAI treatment.

#### A. Objectives

-Determine the effectiveness of BFR on traditional PT for non-operative management of FAI

#### B. Hypotheses / Research Question(s)

Blood flow restriction therapy, when added to traditional physical therapy, can improve isometric strength in the non-operative treatment of Femoroacetabular impingement

- 1) Does the addition of BFR to non-operative management of FAI improve hip strength and outcomes
- 2) Does the addition of BFR to the post-operative protocol for hip arthroscopy improve patient reported outcomes

### 1.2 Research Significance

Determining the impact of BFR for improving muscular strength of the hip could positively impact rehabilitation recommendations for conservative treatment of hip related problems, including FAI.

### 1.3 Research Design and Methods

Randomized control trial

#### A. Research Procedures

The project will be a randomized control trial where all patients who present to our office with groin based hip pain, radiographic evidence of FAI, and a positive anterior impingement test would be recruited. Two groups will then be separated: one being the traditional physical therapy group, and the other with the addition of BFR to traditional PT.

Standard radiographs would be obtained and would include a standard AP pelvis, Dunn view, and false profile view.

Initial office visit would record the patient's degree of hip flexion, result with anterior impingement testing, alpha angle (on dunn view), lateral center edge angle (on AP pelvis) and anterior center edge angle (on false profile view). Additionally, we would evaluate for the presence of ischial spine sign, cross over sign, and if the proximal femoral physis was present on radiographs. MRI will not be routinely ordered on the initial visit, but if this has already been obtained, the presence of a labral tear based on the radiology report will be recorded.

Demographic data would be collected which would include age, sex, primary sport, duration of symptoms, and previous treatment.

Physical therapy protocol would include traditional PT focusing on core and gluteal strengthening. Additionally, avoidance of activities and exercises that result in pain or high hip flexion and internal rotation would be recommended. After 6 weeks, if the patient remained symptomatic, an ultrasound guided intra-articular hip injection would be offered to the patient. If the patient remained persistently symptomatic, then hip arthroscopy would be offered to the patient.

**B. Data Points**

- Objective strength measurements utilizing a hand held dynamometer
- Results of PROM.
- Demographic and surgical data

**C. Study Duration**

- 1 year – total study time,
- Individual commitment – 2 x wk, x 8 weeks involvement in physical therapy program.

**D. Endpoints**

- Patient ops out of study
- Re-injury/Alternate injury
- Completion of 8 week rehab program

**1.4 Preliminary Data**

- Pre-intervention PRO data
- Clinical Exam – determine baseline status

**1.5 Sample Size Justification**

Previous similar studies have recruited 35 to 60 subjects for similar studies looking at functional outcomes with BFR treatment. We are conducting an a priori power analysis with Rutgers RUBIES to determine the sample size required for 80% power with an alpha of 5%.

**1.6 Study Variables**

**A. Independent Variables, Interventions, or Predictor Variables**

1. Physical Therapy Protocol
  - a. Standard PT protocol focusing on core and glute strengthening would begin 2x/week for duration of 8 weeks.
2. BFR protocol

- a. If patient randomized to BFR arm, begin with 50% limb occlusion pressure at proximal leg.
- b. *Start with quadriceps contractions, step-ups, single and double squat, monster walk, then progress to wall squats, clam shell, leg press, glute bridges and stationary biking.*
- c. *Four sets of each activity (30/15/15/fatigue). 30 second rest in between.*  
*- 2x/week for 8 weeks*

**B. Dependent Variables or Outcome Measures**

- a. Isometric strength- hip flexion,
- b. Muscular endurance (repetitions to fatigue [RTF]; 20% maximum; with and without 50% occlusion) were measured before and after training.
- c. ROM
- d. VAS initial, week 2, 4, 8.
- e. PROMIS-10, modified harris hip scope, IHOT-12

**1.7 Drugs/Devices/Biologics**

**A. Schedule and Administration**

NA

**B. Drug/Device Accountability and Storage Methods**

NA

**1.8 Specimen Collection**

NA

**A. Primary Specimen Collection**

- **Types of Specimens:**
- **Annotation:**
- **Transport**
- **Processing:**
- **Storage:**
- **Disposition**

**B. Secondary Specimen Collection - NA**

:

- **Types of Specimens:**
- **Annotation:**
- **Transport:**
- **Storage**
- **Disposition:**

**1.9 Data Collection**

**A. Primary Data Collection**

Data will be collected by Physical Therapists during their treatment visits at a UOA physical therapy clinic.

- **Location:** - UOA, Non-Rutgers approved facility, recorded via RedCap Survey Tool
- **Process of Data Collection:**Data will be collected by physical therapists providing standard patient care. .
- **Timing and Frequency:** Pre/Post intervention, PROMs – Pre, 2, 4, 8 weeks.
- **Procedures for Audio/Visual Recording:** NA
- **Study Instruments:**
  - **VAS** – Visual Analog Pain Scale – ( 0-10)
  - **PROMIS-10** – Pre/Post intervention
  - **Modified Harris Hip Score** – Pre/Post intervention

- IHOT-12 – Pre/Post Intervention
- **Ethnographic Studies, Interviews, Or Observation:**
- **Subject Identifiers** – Upon volunteering for the study, patients will be assigned a study number. All data collected will be associated with the no personal identifiers.

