**Data Abstraction Form(s):**

**1.10 Timetable/Schedule of Events**

Subjects will be advised of the study by referring Physician. Potential participants will be referred to physical therapy and notified of study. After private review, and answering of all questions, the subjects will volunteer to participate, and sign consent form. Pre-Intervention PROMs will be completed prior to involvement in the study. Supervising physical therapists will collect Baseline pre-intervention assessment including measurement of ROM, strength and endurance as measured by Microfet handheld dynamometer @weej 2, 4, 8 week intervals.. VAS will be collected by PT @ week 2, 4, 8 week intervals. PROMs will be repeated at the completion of physical therapy program.

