**F. Minimizing Risks of Harm**

All therapy-related activities will be performed by trained medical professionals with years of training. All collected data will be recorded directly to REDCap by study members at the time of the research visit. Access to REDCap will be password-protected and limited to only study team members, and data recording will be performed on password-protected computers at UOA sites.

All supervising therapists have received formal training with the use of BFR and will utilize the pressure cuff appropriately. Subjects will be evaluated after each use and appropriate care provided if there are any associated injuries.

- **Certificate of Confidentiality NA**
- **Provisions to Protect the Privacy Interests of Subjects**

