## 6.0 Data Management Plan

### 6.1 Data Analysis

Rutgers RUBIES will conduct a priori power analysis for determining the appropriate sample size. Functional outcome measures (ROM, strength, muscle endurance) will be analyzed via Student's t test. PROMs (IHOT, mHHS, VAS, PROMIS-10) will be analyzed via Wilcoxon unranked sum test.

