### 6.2 Data Security

All collected data will be recorded directly to REDCap by study members at the time of the research visit. Access to REDCap will be password-protected and limited to only study team members, and data recording will be performed on password-protected computers at UOA sites. Paper copies of data will not be kept. Data will be kept on REDCap for 6 years after which it will be deleted.

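### A randomized patient who is re-injured or leaves physical therapy without withdrawing consent has no planned route to a week-8 outcome

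*Protocol*

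**What the plan says.** - **End of a patient's course.** Section 1.3.D, headed Endpoints, has three entries: opting out, "Re-injury/Alternate injury", and completing the 8-week programme. Outcome variables are listed elsewhere, in 1.6.B.
- **Where data come from.** Section 1.9.A: "Data will be collected by Physical Therapists during their treatment visits at a UOA physical therapy clinic".
- **Final PROMs.** Section 1.10: "PROMs will be repeated at the completion of physical therapy program".
- **Week 8 as a time point.** Section 1.10: "VAS will be collected by PT @ week 2, 4, 8 week intervals". The same section gives weeks 2, 4 and 8 for strength, ROM and endurance. One line of 1.9.A gives "PROMs – Pre, 2, 4, 8 weeks", but the instrument list beneath it gives only pre- and post-intervention for PROMIS-10, the modified Harris Hip Score and iHOT-12.
- **Recording.** Section 4.7.F: "All collected data will be recorded directly to REDCap by study members at the time of the research visit". Section 6.2 repeats this and adds that "data recording will be performed on password-protected computers at UOA sites". Neither section defines a research visit.
- **Analysis.** Section 6.1: "Functional outcome measures (ROM, strength, muscle endurance) will be analyzed via Student's t test". PROMs get a Wilcoxon test.

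**The concern.** Re-injury and leaving therapy happen after randomization. If the final measurement exists only for patients still attending, the groups compared at week 8 are no longer the groups that were randomized. Where the losses differ between arms and are related to how patients are doing, the comparison is biased. The bias would favour BFR if patients doing badly leave that arm more often, and would go against BFR if patients who recover early do so.

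This belongs in the protocol. An SAP can define the analysis set or use week-2 and week-4 values to impute, but it cannot supply a week-8 value that nobody collected. With 26 subjects in total (section 4.3.A), a few such patients matter.

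**Working it through.** **Step 1: follow three kinds of patient through the text.**

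- *Re-injured.* Section 1.3.D treats this as an endpoint. Therapy visits stop, and they are the only collection setting in 1.9.A. The completion that triggers final PROMs in 1.10 does not occur. No other visit is scheduled, so there is no planned route to week 8.
- *Leaves therapy altogether, consent not withdrawn.* Not named in 1.3.D, but the collection setting and the PROM trigger fail in the same way. The gap is inferred from the route of collection, not from a stopping rule.
- *Stops only the cuff.* Standard therapy continues twice weekly for 8 weeks (1.6.A), so this patient still has treatment visits and can complete the programme. There is no gap.

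Two cases lie outside the point. Opting out of the study may properly end data collection. The injection offered after 6 weeks (1.3.A) is not listed as an endpoint. Week-2 and week-4 VAS and strength may exist for an early stopper.

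**Step 2: what could be at stake.** The protocol gives 26 subjects (4.3.A), and 80% power at an alpha of 5% (1.5). It gives no effect size, SD, sidedness, allocation ratio or dropout rate, so 26 cannot be reproduced. *Assumed here:* 13 per arm, two-sided t test at 5%, one to three stoppers, and stopping governed by a score with correlation ρ to outcome (ρ > 0 means poor responders stop).

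Bias under no true effect: the expected largest of 13 standard normal values is 1.668. Removing the single worst patient therefore shifts the mean of the other 12 by 1.668/12 = 0.139 SD. At ρ = 0.5 the shift is half that, about 0.07 SD. Simulation (200,000 runs) agrees and extends this:

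| Stoppers, BFR v control | ρ | Bias in SD (+ favours BFR) | False significant results favouring BFR (nominal 2.5%) |
|---|---|---|---|
| 1, 2, 3 v 0 | 0 | about 0 | 2.5% |
| 1, 2, 3 v 0 | 0.5 | +0.069, +0.130, +0.184 | 3.7%, 5.1%, 6.5% |
| 1, 2, 3 v 0 | 1 | +0.139, +0.256, +0.370 | 6.0%, 10.4%, 16.0% |
| 1, 2, 3 v 0 | −0.5 | −0.069, −0.131, −0.184 | 1.8%, 1.2%, 0.9% |
| 1, 2, 3 v 0 | −1 | −0.139, −0.257, −0.370 | 1.3%, 0.7%, 0.3% |
| 3 v 1 | 0.5; 1 | +0.113; +0.230 | 4.8%; 11.4% |
| 3 v 1 | −0.5; −1 | −0.114; −0.229 | 1.5%; 1.1% |
| 1, 2 or 3 in each arm | same in both | within 0.002 of 0 | not computed |

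The 3 v 1 row follows from the others: 0.370 − 0.139 = 0.231, against 0.230 simulated.

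**Step 3: power.** For 13 v 13, the noncentral t gives 80% power at d = 1.145, with noncentrality d√(n₁n₂/(n₁+n₂)) = 1.145 × √6.5 = 2.92. At that d:

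- losing 1, 2 or 3 from one arm gives 78.2%, 76.2%, 73.8%;
- losing 1, 2 or 3 from each arm gives 76.5%, 72.4%, 67.8%.

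These hold only if 26 is the evaluable number; the protocol does not say whether it allows for dropout.

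**The case against.** **The gap is read into the text.** The heading Endpoints is undefined. Completers also reach an endpoint and are measured at it, so reaching one cannot by itself mean that there is no final assessment. Week 8 is a calendar time point for several measures, a REDCap survey tool is named in 1.9.A, and a research visit is mentioned. A site could well obtain a week-8 value. This stands as far as it goes: the protocol does not forbid such a measurement. It also does not plan one, because it schedules no visit apart from therapy and places recording at the clinic sites.

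**A reader might infer that patients who stop the cuff are lost too, and so that the bias favours BFR.** The protocol does not support this. Those patients stay in standard therapy and are still measured. Leaving therapy altogether is open to both arms. The soreness, bruising and tingling listed in 4.7.A might lead some BFR patients to leave entirely, but the protocol gives no rate and nothing establishes a direction.

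**The magnitude is assumed.** This is correct. The 16.0% needs exactly the three worst of 13 BFR patients to leave and no controls. The t-test figures apply to the functional outcomes; the Wilcoxon test for PROMs was not modelled.

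**The remedy helps least where the hypothesis lies.** Section 1.1.B concerns isometric strength, and a re-injured patient may be unfit for testing. This stands for strength in those patients. It does not stand for PROMs and VAS, or for patients who leave uninjured.

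**Conclusion.** The point holds in a limited form. Read together, 1.3.D, 1.9.A and 1.10 leave a randomized patient who is re-injured, or who leaves therapy without withdrawing consent, with no planned route to a week-8 outcome. It would be too strong to say that the protocol discards all data on such patients, or that the trial is biased towards BFR: earlier measurements may exist, and the direction is unknown.

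Size is also unknown. Under the stated assumptions the bias lies between −0.37 and +0.37 SD. It averages zero when loss is unrelated to outcome, or when equal numbers leave both arms for the same reason. Severity is low to moderate. It is worth correcting because the change is cheap and an uncollected week-8 value cannot be recovered later.

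**What to change.** - **1.3.D:** state that re-injury or leaving therapy ends study treatment only, and that only withdrawal of consent to data collection ends follow-up.
- **1.9 and 1.10:** set the final assessment at 8 weeks from randomization, whether or not therapy was completed. Collect PROMs and VAS from everyone, by REDCap survey if the patient does not attend. Test strength, ROM and endurance if safe. Remove the conflict over PROM timing in 1.9.A.
- **4.7.F and 6.2:** align the recording wording so that a remote survey is allowed.

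**Cost:** text edits in these five sections, a check of the consent form (not shown), and one visit or survey per early stopper. That is 1 to 6 patients if one to three stop in one or both arms.

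**Downsides:** the estimate becomes the effect of being assigned to BFR, which may be smaller than the effect in completers. Strength may still be missing in patients too injured to test.

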**B. Secondary Data Collection NA**

- **Type of Records:**
- **Location**
- **Inclusion/Exclusion**

**Data Abstraction Form(s):**

**1.10 Timetable/Schedule of Events**

Subjects will be advised of the study by referring Physician. Potential participants will be referred to physical therapy and notified of study. After private review, and answering of all questions, the subjects will volunteer to participate, and sign consent form. Pre-Intervention PROMs will be completed prior to involvement in the study. Supervising physical therapists will collect Baseline pre-intervention assessment including measurement of ROM, strength and endurance as measured by Microfet handheld dynamometer @weej 2, 4, 8 week intervals.. VAS will be collected by PT @ week 2, 4, 8 week intervals. PROMs will be repeated at the completion of physical therapy program.

**2.0 Project Management**

Project management will be overseen by the supervisor of physical therapy, PI and study coordinator. Each will be involved in regular review of therapy, adherence to study guidelines and reporting of any adverse incidents.

**2.2 Research Staff Training**

Each member of the study team will participate in a group educational session to ensure continuity of care and commitment to the study.

**2.3 Other Resources**

UOA offers ample room and equipment to conduct the processes of the study.

### 3.0 Multi-Center Research

### 4.0 Subject Considerations

#### 4.1 Subject Selection and Enrollment Considerations

##### A. Method to Identify Potential Subjects

Patients with FAI, who meet defined study criteria, present for care with a UOA physician will be invited to participate in the study..

##### B. Recruitment Details

Physicians will identify potential subjects and share notification of study brochure. Patients will be referred to physical therapy. Physical therapists will review study details, share protocol, and answer questions that may be associated with the study. After all questions have been answered, subjects may volunteer to participate in the study by signing a consent to participate form with the supervising physical therapist.

##### C. Subject Screening

Patients will be screened for inclusion by participating surgeons.

###### ▪ Inclusion Criteria

- Age 18 yrs or older
- FAI diagnosed in office
- Groin pain and + anterior impingement testing

▪

###### ▪ Exclusion Criteria

- History of DVT, VTE, or clotting disorder
- History of CRPS or current radicular leg pain
- Trochanteric bursitis as primary diagnosis
- Pre-existing hip condition (SCFE, perthes, AVN)
- Osteoarthritis (Tonnis >2) on xrays
- Stress fracture

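### The cuff is said to restrict arterial as well as venous flow, but the only vascular exclusion is venous or clotting history, so a patient with known lower-limb arterial disease is eligible as written

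*Protocol*

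**What the plan says.** **Mechanism.** Section 1.1 describes a tourniquet that acts to "partially occlude the arterial and fully occlude the venous flow during exercise". It then gives the consequence: "Compression of the vasculature results in muscle hypoxia, blood pooling, and increased intramuscular pressure below the cuff".

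**Dose.** Section 1.6 A tells therapists to "begin with 50% limb occlusion pressure at proximal leg". Sessions run twice weekly for 8 weeks, and the last of four sets of each activity is taken to fatigue.

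**Eligibility.** Section 4.1 C has three inclusion lines: age 18 or over with no upper limit, an office diagnosis of FAI, and groin pain with a positive anterior impingement test. It has six exclusion lines, of which one is vascular: "History of DVT, VTE, or clotting disorder".

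**Screening.** Section 4.1 C says "Patients will be screened for inclusion by participating surgeons". Section 1.4 lists a clinical exam to "determine baseline status".

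**Testing under occlusion.** Section 1.6 B lists muscular endurance "with and without 50% occlusion) were measured before and after training", without saying which arm or arms are tested with the cuff on.

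**The concern.** The protocol names two vascular actions of the cuff, one on arterial inflow and one on venous outflow. Its vascular exclusion addresses only venous thromboembolism and clotting. A leg whose arterial supply is already reduced is one in which further arterial restriction and hypoxia during exercise to fatigue would be a natural worry, and the eligibility rules do not mention it.

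What is at stake is the safety of an individual participant. Section 4.7 G states that participants gain no direct benefit, which makes an avoidable exposure harder to justify. Estimation and testing are not affected. Eligibility belongs in the protocol, so a separate statistical analysis plan would not be expected to fill this gap.

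**Working it through.** This is mainly a check of text against text, with one small calculation.

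**Step 1. Try a patient against the criteria.** Take an adult with FAI, groin pain, a positive impingement test, and known or symptomatic lower-limb arterial disease.

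| Section 4.1 C line | Result for this patient |
|---|---|
| Inclusion: adult | met |
| Inclusion: FAI diagnosis | met |
| Inclusion: groin pain and positive test | met |
| Exclusion: venous thrombosis or clotting history | not triggered |
| Exclusion: CRPS or radicular leg pain | not triggered |
| Exclusion: primary trochanteric bursitis | not triggered |
| Exclusion: earlier hip condition (SCFE, Perthes, AVN) | not triggered; these are hip conditions and do not cover limb arterial disease |
| Exclusion: osteoarthritis above the Tonnis limit | not triggered |
| Exclusion: stress fracture | not triggered |

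Three of three inclusion lines are met and none of six exclusion lines applies, so the patient is eligible.

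**Step 2. Look for the safeguard elsewhere.**
- Section 1.3 A details the first office visit: hip flexion, impingement testing, and radiographic angles and signs. No vascular item appears.
- Section 1.4 lists a baseline clinical exam without describing its content.
- Section 4.1 C gives screening to the surgeons, but the criteria they apply have no arterial term.
- Section 4.7 F relies on trained therapists and on evaluation after each cuff use, which comes after exposure.
- Section 1.3 D ends participation on "Re-injury/Alternate injury", which comes after harm.
- No section contains an investigator-discretion or general contraindication clause.

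**Step 3. Bound the exposure.** Inputs from Section 1.6 A: 2 sessions per week and 8 weeks.

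Maximum cuff sessions per BFR patient = 2 × 8 = 16.

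This is an upper bound. It falls if the patient withdraws, is injured, or is stopped after a post-use evaluation.

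**Step 4. What cannot be computed.** The protocol gives neither the number of recruits likely to have arterial disease nor the chance of injury at this pressure. No value is assumed here. Total enrolment is 26 (Section 4.3 A).

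**The case against.** The strongest reply is that the hazard is inferred. No section says that arterial disease is a contraindication to BFR, or that 50% of limb occlusion pressure would harm such a leg. The pressure is set relative to the limb's own occlusion pressure and is not a fixed value, and Section 1.1 calls the tourniquet non-occlusive. Sections 1.1 and 4.1 C do not contradict each other; the exclusion list is simply shorter than it could be. The trial is small, and its recruits have impingement-type groin pain without advanced osteoarthritis. The protocol records their primary sport, so arterial disease is likely to be rare. Surgeons screen, therapists are trained in BFR, and each use is followed by an evaluation.

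Most of this stands, and it limits the weight of the point. It does not remove the gap. The sentence that uses the word non-occlusive also states partial arterial occlusion. A surgeon may well notice known arterial disease, but no written rule says to exclude it.

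Three stronger readings are tempting, and the documents do not support them:

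- **That PT-only patients certainly wear the cuff at testing.** Section 1.6 B does not assign testing under occlusion by arm, and Section 1.10, which schedules endurance testing, does not mention occlusion. Silence does not establish that controls are cuffed. The two sections also differ on when endurance is measured (before and after training, against baseline and weeks 2, 4 and 8), so no firm count of occluded tests can be given.
- **That the sponsor judged there to be no risk from existing conditions.** Section 4.7 A marks that field as not applicable, but many template fields are marked the same way. It carries little weight.
- **That the missing upper age limit means older patients with vascular disease will be enrolled.** It makes them eligible; it does not show that they would be recruited.

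**Conclusion.** The gap is real but of low severity. As written, a patient with known or symptomatic lower-limb arterial disease may be enrolled and, if randomised to BFR, could receive up to 16 sessions with a cuff that the protocol says restricts arterial flow. This rests on a literal reading of the criteria and on the mechanism in Section 1.1; it needs no outside source. That such a leg is at added risk is an inference from the mechanism. The protocol does not measure that risk, and it is probably small in this population.

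A reader might infer that the trial is unsafe or that its results would be compromised. Neither follows: the documents show no demonstrated hazard, and the treatment comparison is not affected.

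**What to change.** Add one line to the exclusion criteria in Section 4.1 C: known or symptomatic lower-limb arterial disease. Apply it to every patient, whichever arm they might enter, at the surgeon's existing screen. It should come before randomisation and before any endurance test done under occlusion, because Section 1.6 B leaves open who is tested with the cuff.

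The cost is one line of text and one history question. No new test, visit or analysis is needed. The downside is that a few patients may be turned away.
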